9.3 HRQoL Tools

The Kids ITP tool (KIT) will be performed at Baseline/Screening, at Study Visits Week 1, Week 4, Week 12, and 1 year. The KIT is the first disease-specific health related quality of life measure developed for ITP, specifically for use with children. It contains a child self-report version (to be completed by children ages 7 and older), a parent proxy version (to be completed by parents of children age 2 and older), and parent version (to assess parental impact of ITP - all ages). Each version consists of 26 items, and a single overall score is obtained. Scores range from 0 to 100: a higher score represents better quality of life or, as with the parental impact version, less burden. Response options are on a 5-point Likert-type scale ranging from "never" to "always", and the timeframe of interest is the "past week". KIT will be administered in English, Spanish, or Quebec French.

Assessment of global change will be performed at Week 1, Week 4, Week 12, and 1 year using the Parent Proxy-Report and Child Self-Report Change Scales.

Assessment of fatigue will be performed at Baseline/Screening, at Study Visits Week 1, Week 4, Week 12, and 1 year using the Fatigue Scale-Child (FS-C to be administered by children ages 7 to 12 years), the Fatigue Scale-Adolescent (FS-A teens ages 13 and older), and the Fatigue Scale-Parent (FS-P to be completed by parents of children of all ages). Each item has a 5-point Likert-type format; total scale intensity ratings have been rescaled so that they range from 0 (no fatigue symptoms) to 100 (highest possible fatigue score). All of the tools have been evaluated for face, content, and construct validity and for internal consistency. The tools take five minutes to complete. Fatigue scales will be administered in English.

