To address the primary objective, we will first test for normality of the distribution of the proportion of platelet responders. If the assumption of normality is upheld, a one-sided Cochran-Mantel-Haenszel (CMH) test, at alpha=0.025, will be used to compare the proportion of platelet responders between the two arms. If the normality assumption is violated, then a one-sided Fisher's exact test will be used. The monitoring boundaries and levels of significance for the interim and final analyses of the primary endpoint are detailed in Table 16A. If a monitoring boundary is crossed in an interim analysis, an independent Data Safety Monitoring Board (DSMB) will make a non-binding recommendation regarding trial conduct or potential closure. In the final analysis, we will reject the null hypothesis if the upper (efficacy) boundary z-value of 1.99302 is crossed; in that case, it will be reasonable to conclude that the rate of platelet response is significantly greater in patients treated with eltrombopag than standard first-line treatments. Otherwise, we will conclude that there is insufficient evidence to support superiority of eltrombopag over standard first-line treatments. All randomized patients will be analyzed in the ITT analysis.

Selection of platelet measurements for the determination of platelet response.

All platelet counts will be reported, and the four measurements closest in time to Weeks 6, 8, 10, and 12 will be selected for the determination of the primary endpoint. Within a sliding one-week window, only one measurement can be selected. Patients who have <3 platelet measurements due to missing data will be classified as non-responders.

c. Analysis of Secondary Endpoints

Analyses of all secondary endpoints will be performed in the subset of evaluable patients. To determine the effects of missing data, sensitivity analyses will be performed using two approaches: a) assuming missing at random; and, b) assuming missing not at random. For each secondary endpoint, the assumption of normality will be tested. If violated for binary endpoints, a Fisher's exact test will be used. If violated for continuous endpoints, a Wilcoxon rank-sum test will be used.

To address secondary objective 3.2.1, the Cochran-Mantel-Haenszel test will be used to compare the proportion of patients with poor WHO Bleeding Score and poor Modified Buchanan Score between the two arms.

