To address secondary objective 3.2.2, an ANCOVA model will be used to compare the number of rescue therapies between the two arms.

To address secondary objective 3.2.3, the observed proportion and 95% confidence interval of platelet responders will be calculated in the subset of patients who required a rescue treatment during weeks 1-2 of the study.

To address secondary objective 3.2.4, the Cochran-Mantel-Haenszel test will be used to compare the proportion of patients who do not need ongoing treatment at 12 weeks and 6 months between the two arms.

To address secondary objective 3.2.5, the Cochran-Mantel-Haenszel test will be used to compare the proportion of patients with a treatment response at one year between the two arms.

To address secondary objective 3.2.6, an ANCOVA model will be used to compare the number of 2nd-line therapies between the two arms

To address secondary objective 3.2.7, an ANCOVA model will be used to compare the absolute change from baseline in percentage of regulatory T cells at 12 weeks and 1 year between the two arms

To address secondary objective 3.2.8, KIT scores will be calculated as per the methods described in Klaassen et al.²⁸ Spaghetti plots will be used to visualize the KIT scores over time per patient by treatment arm. An ANCOVA model will be used to compare the absolute change from baseline in KIT overall score at 1 week, 4 weeks, 12 weeks, and 1 year between the two arms. An ANCOVA model will be used to compare the Change Scale score at 1 week, 4 weeks, 12 weeks, and 1 year between the two arms.

To address secondary objective 3.2.9, fatigue scores will be calculated as per the methods described in Hockenberry et al.²⁹ All measures will be rescaled from 0 (no fatigue) to 100 (high fatigue) for consistency in scoring. Spaghetti plots will be used to visualize the fatigue scores over time per patient by treatment arm. The PROMIS tired question: “My child (I) got tired easily never to almost always” will be used as an anchor with severe fatigue defined as “often” or “almost always” with moderate fatigue being “sometimes”. An ANCOVA model will be used to compare the absolute change from baseline in fatigue at 1 week, 4 weeks, 12 weeks, and 1 year between the two arms.

To address secondary objective 3.2.10, an ANCOVA model will be used to compare iron indices at 12 weeks, 6 months, and 1 year between the two arms

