Global02_PXR1	In general, would you say your child's quality of life is:.....	 5	 4	 3	 2	 1
Global03_PXR1	In general, how would you rate your child's physical health?.....	 5	 4	 3	 2	 1
Global04_PXR1	In general, how would you rate your child's mental health, including mood and ability to think?	 5	 4	 3	 2	 1
		Never	Rarely	Sometimes	Often	Always
PadGlobal01_PXR1	How often does your child feel really sad?	 5	 4	 3	 2	 1
		Always	Often	Sometimes	Rarely	Never
PadGlobal02_PXR1	How often does your child have fun with friends?	 5	 4	 3	 2	 1
PadGlobal03_PXR1	How often does your child feel that you listen to his or her ideas?	 5	 4	 3	 2	 1
	In the past 7 days...					
		Never	Almost Never	Sometimes	Often	Almost Always
PadGlobal04_PXR1	My child got tired easily.....	 1	 2	 3	 4	 5
PadGlobal05_PXR1	My child had trouble sleeping when he/she had pain.....	 1	 2	 3	 4	 5

CHANGE SCALE – PARENT PROXY-REPORT

Instructions: Please answer the questions below about your child.

Since the start of the study, how has your child's overall quality of life related to ITP changed?

- Much worse
- Worse
- A little worse
- No change
- A little better
- Better
- Much better

CHANGE SCALE – CHILD SELF-REPORT

Instructions: Please answer the questions below.

Since the start of the study, how has your overall quality of life related to ITP changed?

- Much worse
- Worse
- A little worse
- No change
- A little better
- Better
- Much better

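### The Change Scale's ANCOVA names no covariates and would probably give way to an unadjusted rank-sum test, leaving the randomisation strata and baseline KIT unused (minor)

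*Combined protocol and SAP*

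**What the plan says.** All references are to the combined protocol and SAP.

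- **Instrument (Appendix A2, Change Scale).** The parent form asks "Since the start of the study, how has your child's overall quality of life related to ITP changed" and offers seven ordered answers, from much worse to much better. A child self-report form asks the same of the patient.
- **Timing (section 9.3).** "Assessment of global change will be performed at Week 1, Week 4, Week 12, and 1 year". Because the question is about change since study start, there is no baseline form.
- **Analysis (section 16.c, objective 3.2.8).** "An ANCOVA model will be used to compare the Change Scale score at 1 week, 4 weeks, 12 weeks, and 1 year". No covariate or scoring is given, and the sentence does not say whether the parent or the child form is meant.
- **Normality rule (section 16.c).** "For each secondary endpoint, the assumption of normality will be tested". "If violated for continuous endpoints, a Wilcoxon rank-sum test will be used". The test, its level and its target (raw values or residuals) are not stated.
- **Baseline information available.** "The Kids ITP tool (KIT) will be performed at Baseline/Screening, at Study Visits Week 1, Week 4, Week 12, and 1 year". The proxy form has a lower age limit: "a parent proxy version (to be completed by parents of children age 2 and older". Sections 4 and 16 stratify randomisation by three age groups and two up-front treatment categories, giving six strata.
- **Status.** Objective 3.2.8 (secondary) names the scale beside the KIT. Secondary endpoint 5.2.8 lists only the KIT overall score; the Change Scale appears as an endpoint only under exploratory 5.3.2.

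**The concern.** An ANCOVA is useful here for what it adjusts for. The KIT has its own baseline, but the Change Scale does not, so its covariates have to be named, and they are not. A seven-category item will also seldom pass a normality test, so the stated ANCOVA may never be the analysis performed. Its replacement uses neither the factors the trial randomises by nor the baseline KIT, which indicates how much room each child had to improve.

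At stake are the precision of one of the two measures named in objective 3.2.8, and whether its result comes with an adjusted effect size. The route to the final test is also left to an undefined, data-dependent choice.

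**Working it through.** The documents give no power, SD, effect size or sample size for the Change Scale, so there is no stated figure to reproduce. Two questions can be checked by simulation.

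**1. Would the normality rule trigger?**

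Assumptions: latent normal values rounded and clipped to 1–7, with mean 4 to 5.5 and SD 1.0 to 2.0; tests at 5%. Percentages are simulated trials in which normality is rejected.

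| What is tested | Rejected |
|---|---|
| Raw scores, Shapiro-Wilk, n = 49 to 162 | 98.5–100% (100% at n ≥ 98) |
| Raw scores, Anderson-Darling, n = 49 to 162 | 100% |
| Raw scores, skewness-kurtosis test, n = 147 | 3–96% |
| Residuals, arm only, Shapiro-Wilk, n = 147 | 100% |
| Residuals, arm + strata, Shapiro-Wilk, n = 147 | 32–100% |
| Residuals, arm + strata + baseline KIT, Shapiro-Wilk, n = 147 | 5–91% |

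Rounding to seven values is enough to fail Shapiro-Wilk or Anderson-Darling on raw scores, even when the underlying variable is exactly normal. With no covariates named, the arm-only row is the residual check closest to the plan as written. The switch is therefore nearly certain with those tests on raw scores or arm-only residuals, and uncertain on the other readings.

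**2. What does the unadjusted test lose?**

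Inputs: 98 + 49 = 147 patients, the informative counts in section 4, used here as a stand-in for survey completers; six strata; two-sided 5%; assumed latent effect 0.5 SD. The correlation r between baseline KIT and the latent response is also assumed, since no document gives it.

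*First simulation* (600 trials per setting, modest stratum effects):

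| r | Rank-sum | Adjusted proportional odds | Gain |
|---|---|---|---|
| 0.3 | 76.0% | 81.0% | 81.0 − 76.0 = 5.0 points |
| 0.5 | 77.0% | 87.8% | 87.8 − 77.0 = 10.8 points |

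The Monte Carlo standard error of one power figure is about √(0.8 × 0.2 / 600) = 1.6 points. Type I error at r = 0.5 was 5.2% (proportional odds) and 5.8% (rank-sum).

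*Second simulation* (2,000 trials per setting; latent SD 1.5 and shift 0.75, so 0.75 / 1.5 = 0.5 SD). Adjusted linear ANCOVA on arm, baseline KIT and strata:

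| Latent variance explained by KIT (r = √) | By strata | Rank-sum | Adjusted linear | Gain |
|---|---|---|---|---|
| 0% (0) | 0% | 76.7% | 76.6% | about 0 |
| 10% (0.32) | 5% | 76.1% | 83.9% | 7.8 points |
| 20% (0.45) | 5% | 76.2% | 87.9% | 11.7 points |
| 30% (0.55) | 10% | 76.1% | 93.7% | 17.6 points |

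Simulated type I error was 3.5 to 5.9% for all methods.

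*No correlation, all three methods:* rank-sum 78%, adjusted linear 79%, proportional odds 80%. Adjustment costs nothing when baseline KIT is uninformative.

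*Choice of model:* a further run of adjusted linear ANCOVA gave 82% at r = 0.3 and 88–89% at r = 0.5, against 81% and 88% for proportional odds above. The gain comes from the covariates, not from the choice between these two models.

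**The case against.** A reader might infer more than the documents support, in four ways.

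- **That the planned comparison is invalid or biased.** It is not. Under randomisation the rank-sum test is valid, and it suits ordered categories. Only efficiency and an adjusted estimate are lost.
- **That ANCOVA is impossible without the item's own baseline, or that the plan excludes KIT and strata.** ANCOVA can adjust for other baseline variables. Section 16.c leaves the covariates unspecified and does not rule any out. They are certainly unused only if the rank-sum fallback is reached.
- **That the fallback is certain.** The normality test and its target are unnamed, and some readings trigger it much less often. The rule is written for secondary endpoints and its fallbacks cover binary and continuous ones. It reaches this ordinal item only through objective 3.2.8 and because ANCOVA treats the score as continuous. Endpoint 5.3.2 lists the scale as exploratory.
- **That proportional odds is required.** An adjusted linear ANCOVA recovers about the same power.

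Two further objections stand. The size of the gain depends on assumed correlations; with r = 0.3, stratum effects added almost nothing in one check (77% against 82% with or without them). And 147 is the count for the primary endpoint. Survey numbers may be lower, given the reading and language exclusions in sections 6.3 and 9.3 and the option in 16.d to halt a poorly returned survey.

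The exploratory listing does not dispose of the point. Section 16.c, under 3.2.8, is the only place that assigns the scale an analysis; the text in 16.d for objective 3.3.2 covers KIT and fatigue scores as change from baseline, which this item cannot have.

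**Conclusion.** The point holds as a minor one. The Change Scale's ANCOVA is under-specified. If the normality rule governs the scale and a usual test is run on raw scores, the analysis performed would almost always be an unadjusted rank-sum test, which discards baseline KIT and the randomisation factors.

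The cost is precision only: nothing if baseline KIT is unrelated to the response, and about 5 to 11 power points at assumed correlations of 0.3 to 0.5. The largest simulated gain, about 18 points, needed KIT and strata together to explain 40% of the latent variance and should not be taken as the expected size. All of these figures assume a 0.5 SD effect and 147 respondents.

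**What to change.** In section 16.c, under objective 3.2.8, replace the Change Scale sentence with wording such as:

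> The parent-proxy Change Scale (seven ordered categories) will be compared between arms at each visit by a proportional-odds model with terms for arm, age group, up-front treatment status and baseline KIT parent-proxy score, with a missing-indicator for any absent baseline KIT (child under 2, no translated form, or not completed). The common odds ratio and its 95% CI will be reported. This endpoint is exempt from the normality check.

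An adjusted linear ANCOVA with the same terms is an acceptable alternative if category scores are stated. One of the two should be fixed in advance.

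Reconcile the scale's status between objective 3.2.8 (secondary) and endpoint 5.3.2 (exploratory), and say where the child self-report form is analysed.

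The cost is SAP wording only, with no new data or visits. The downside is reliance on proportional odds, which a table of the seven categories by arm would help to check. The other ANCOVA endpoints in 16.c share the unnamed covariates and the normality rule; this edit does not settle those.
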